2. STUDY OBJECTIVES

2.1 Primary Aim & Hypothesis

Primary Aim: To evaluate the relative contributions of intraoperative chemical and mechanical power on postoperative pulmonary complications within seven days after surgery.

Primary Hypothesis: Compared to intraoperative mechanical power, chemical power contributes less to postoperative postoperative pulmonary complications within seven days after surgery.

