3.4.2 Secondary Exposure

Since plateau pressure was not recorded in every patient, dynamic driving pressure will be calculated as peak pressure – PEEP and dynamic mechanical power will be calculated according to the following formula:

$$MP = 0.098 * Vt * RR * (Ppeak - 0.5 * \Delta P_{insp})$$

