3.6.2 Inferential statistics

Primary aim:

We will summarize intraoperative chemical and mechanical power by calculating time-weighted averages for each patient. The influence of the intraoperatively applied time-weighted average chemical and mechanical power on composite postoperative pulmonary complications will be evaluated by multivariable logistic regression – estimating the odds ratios related to the effect of 1 unit increase in chemical or mechanical power. The regression model will be calculated with and without the above-mentioned confounders. We will consider the exclusion of a potential confounder if its inclusion results in a change in the regression coefficients (beta) for both exposures of less than 10%.

Secondary aim 1:

The relationship between varying levels of chemical / mechanical power and postoperative pulmonary complications will be analysed via multivariable logistic regression including cubic splines with up to five knots of chemical and mechanical power. We will further evaluate whether chemical and mechanical power have an upper threshold of harm, whereafter the odds for PPCs increase substantially by means of threshold regression. We will consider a 5% change in slope as clinically relevant, although there is no established minimal clinically important difference for PPCs, and this definition remains arbitrary.

Secondary aim 2:

We will evaluate the interaction between chemical power and mechanical power by implementing an interaction term for the intraoperatively applied time-weighted average mechanical power in the multivariable regression model performed to evaluate the primary aim. Additionally, we will analyse the effect of chemical and mechanical power on PPCs for 5 subsets of the study population stratified by chemical or mechanical power for each of the following patterns: 1) increasing chemical power and matched mechanical power, 2) matched chemical power and increasing mechanical power, 3) increasing chemical power and decreasing mechanical power, and 4) increasing chemical power and increasing mechanical power. Data will also be graphically presented with a 3D surface plot showing chemical and mechanical power on the x- and z-axes and the percentage of PPCs on the y-axis. Therefore, the population will be divided into equally sized groups including an certain fraction of patients of the ranges of both exposures.

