3.6.3 Tables and figures (planned)

Table 1: Patient characteristics

Demographics, respiratory risk factors, coexisting conditions, and surgery characteristics will be descriptively presented, grouped by low, moderate, marked, and substantial chemical power (<25%, 25-50%, 50-75%, and 75-100% quantile of mechanical power).

Table 2: Intraoperative mechanical ventilation parameters (alternatively as figure)

Intraoperative mechanical ventilation parameters will be descriptively presented, grouped by low, moderate, marked, and substantial chemical power (<25%, 25-50%, 50-75%, and 75-100% quantile of mechanical power)

Figure 1: CONSORT diagram

Figure 2: Ranges of chemical, mechanical, and mechanochemical power quartiles

Barplots showing the ranges of time-weighted averages of chemical, mechanical, and mechanochemical power for patients with low (first quartile: <25%), moderate (second quartile: 25-50%), marked (third quartile: 50-75%), and substantial (fourth quartile: 75-100%) power.

Figure 3 a/b (take-away-figure): Chemical and mechanical versus the risk of PPCs.

Smoothed spline regression curves with the odds ratios for each spline presenting the risk for PPCs over the observed ranges of chemical (a), and mechanical power (b).

Figure 4 a/b/c: Stratified analysis of chemical and mechanical power on PPCs

Bar plots on top: a) increasing chemical power and matched mechanical power, b) matched chemical power and increasing mechanical power, c) increasing chemical power and decreasing mechanical power, and d) increasing chemical power and increasing mechanical power. Error bars on bottom: corresponding relative risks of PPC, calculated for each subsample; error bars represent the 95% confidence interval.

Figure 5 (alternative take-away-figure): Chemical and mechanical versus the risk of PPCs

A 3D surface plot with chemical and mechanical power on the x- and z-axes and the percentage of PPCs on the y-axis. The population will be divided into equally sized groups including an applicable fraction of patients of the ranges of both exposures.

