3.6.5 Limitations

We are aware of several limitations of our analyzes. (1) Although the database was derived from trials, our study is observational, meaning we may detect associations but not establish causality. (2) Due to a widespread use of lung-protective mechanical ventilation exposure to higher ranges of mechanical power is presumably rare. (3) The use of supplemental oxygen (FiO₂) is potentially highly confounded by underlying pulmonary risk and patients' intraoperative responses to surgery and mechanical ventilation. (4) The underlying trials used slightly different definitions of postoperative pulmonary complications, adding further variability and potential bias to the results.

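### The primary hypothesis ranks two effects, but the primary analysis plans no contrast between them and no criterion for 'less'

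*Combined protocol and SAP*

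**What the plan says.** Section 2.1 sets the aim of weighing the two exposures against each other and states a directional primary hypothesis: "Compared to intraoperative mechanical power, chemical power contributes less to postoperative postoperative pulmonary complications".

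Section 3.6.2 (primary aim) reduces each exposure to a time-weighted average per patient and fits a logistic model, "estimating the odds ratios related to the effect of 1 unit increase in chemical or mechanical power". It adds: "The regression model will be calculated with and without the above-mentioned confounders". A confounder may be dropped if including it gives a "change in the regression coefficients (beta) for both exposures of less than 10" per cent. That wording implies that both exposures are in the same model.

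On scale, section 3.4.1 prints J/min for chemical power. Section 3.4.2 says that "dynamic mechanical power will be calculated according to the following formula" but prints no unit beside the formula. Figure 2 in section 3.6.3, "Ranges of chemical, mechanical, and mechanochemical power quartiles", plans a combined quantity, which suggests a shared energy scale.

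Section 3.6.4 has no power calculation. No section gives a significance level or margin for the primary hypothesis.

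**The concern.** A claim that one effect is smaller than another needs an estimate of the difference and a measure of its uncertainty. The plan yields up to four odds ratios (two exposures, two models) and stops there. Two separate odds ratios do not settle the comparison: one can be significant and the other not while the data remain compatible with no difference. The ranking can also change with the scale.

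This is a post hoc analysis of data that have already been combined, so prespecification is the main safeguard. Without it, the way of comparing the odds ratios could be chosen once the results are known, and a statement about relative contribution could be published without a test behind it.

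**Working it through.** The documents give no figure to reproduce. The check is first of the text, then illustrative arithmetic.

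**1. Does another part of the plan supply the comparison?**
- The 5% change-in-slope criterion (section 3.6.2) belongs to secondary aim 1, on thresholds.
- The interaction term belongs to secondary aim 2. It asks whether one effect depends on the other exposure, not which effect is larger.
- Figure 4 plans relative risks by subsample, where "error bars represent the 95% confidence interval". It also serves secondary aim 2, and it does not contrast the two effects.
- Section 3.6.5 disclaims causality. A non-causal comparison still has to be made.

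None of these is a test of the primary hypothesis.

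**2. Separate odds ratios do not establish a difference.** Assume odds ratios of 1.01 (SE 0.012) for chemical and 1.04 (SE 0.015) for mechanical power.
- Single tests: z = ln(1.01)/0.012 = 0.83 and ln(1.04)/0.015 = 2.61. Only mechanical power is significant.
- Difference: ln(1.04) − ln(1.01) = 0.0293, with SE = √(0.012² + 0.015² − 2ρ·0.012·0.015).
- For a correlation ρ between the two estimates of −0.3, 0 and +0.3, z = 1.34, 1.52 and 1.81 (two-sided p = 0.18, 0.13 and 0.07).

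**3. The ranking depends on scale.** Assume odds ratios per J/min of 1.03 (chemical) and 1.05 (mechanical).
- With SDs of 2 and 4 J/min, the odds ratios per SD are 1.03² = 1.061 and 1.05⁴ = 1.216.
- With SDs of 4 and 2 J/min, they are 1.03⁴ = 1.126 and 1.05² = 1.103, and the ranking reverses.

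**4. Precision of the contrast.** From the section 3.4.1 formula, the SD of chemical power is 141000 × 1.63×10⁻⁴ × SD(FiO₂) = 22.983 × SD(FiO₂). An assumed FiO₂ SD of 0.10 or 0.20 gives 2.30 or 4.60 J/min. For a joint model without further covariates,

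Var(β_CP − β_MP) ≈ [1/SD_CP² + 1/SD_MP² + 2r/(SD_CP·SD_MP)] / [N·p(1−p)·(1−r²)],

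where r is the correlation between the exposures and p the PPC risk. The detectable ratio of the two odds ratios, larger over smaller, at 80% power and two-sided 5% is exp(2.80·SE).

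Assumed ranges: N 3,000 to 4,000, PPC 15 to 35%, FiO₂ SD 0.10 to 0.20, mechanical power SD 2 to 6 J/min, r from −0.5 to +0.5.

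| Case | N·p(1−p) | SD_CP | SD_MP | r | SE | Ratio |
|---|---|---|---|---|---|---|
| Most precise | 910 | 4.60 | 6 | −0.5 | 0.0075 | 1.02 |
| Middle | 750 | 2.30 | 4 | 0 | 0.0183 | 1.05 |
| Least precise | 382.5 | 2.30 | 2 | +0.5 | 0.0479 | 1.14 |

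Middle case: (0.1893 + 0.0625)/750 = 0.000336, whose square root is 0.0183.

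**5. Does a second condition settle what 'less' means?** Suppose 'less' also required the confidence interval of the mechanical power odds ratio to lie above 1. Assume log-odds per J/min of −0.10 (chemical) and +0.03 (mechanical), N 4,000, PPC 25% and mechanical power SD 4.
- The contrast interval then lies below zero in almost every draw, so the rule reduces to the mechanical power test.
- At r = 0, SE_MP = 1/(4·√750) = 0.0091, and Φ(0.03/0.0091 − 1.96) is about 0.91.
- At r = ±0.5, SE_MP = 1/(4·√(750·0.75)) = 0.0105, and the probability is about 0.81.

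The rule therefore concludes 'less' in 81 to 91% of draws, although the chemical coefficient is more than three times larger in size. The meaning of 'less' when chemical power looks protective has to be stated separately.

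**The case against.** The strongest defence is that the primary aim is one of estimation. Section 1 speaks of evaluating effects and keeps testing language for the thresholds and the interaction. The work is post hoc, unpowered and openly observational. Two odds ratios on what looks like a common energy scale describe relative contributions reasonably well. This stands for the aim, and the planned estimates are usable. It does not cover the sentence labelled as the primary hypothesis, which is directional.

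A reader might infer that the choice between the adjusted and unadjusted model is wholly open. The documents do not support that. Secondary aim 2 refers to a single multivariable model for the primary aim, section 3.6.2 gives a rule for dropping confounders, and section 3.6.5 says that oxygen use "is potentially highly confounded by underlying pulmonary risk". The adjusted model is the natural reading. What is missing is the explicit statement, which matters less than the missing contrast.

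A reader might also infer that the plan would wrongly support its hypothesis half the time when the effects are equal. Either of two such estimates is the smaller in about 50% of datasets by construction, and the plan does not propose to decide by whichever odds ratio is smaller. That figure is not an error rate of this plan.

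Finally, comparing per J/min is a choice that the phrase about relative contributions does not dictate. This is fair. It is proposed below because it matches the per-unit odds ratios already planned.

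**Conclusion.** The point holds on the text alone: the primary hypothesis is comparative, and no part of the plan compares the two effects or says what would count as 'less'. It concerns the primary hypothesis and should be settled before the analysis is run. The unnamed deciding model and the missing unit for mechanical power are smaller gaps in the same paragraphs' logic.

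The documents do not fix a numerical size. The SE range of about 0.008 to 0.048 and the detectable ratio of about 1.02 to 1.14 rest entirely on the assumed sample size, event rate, exposure spreads and correlation, and on a model with no confounders. Adjustment would generally widen them. The finding does not show that either odds ratio would be wrong, or that the hypothesis is false.

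**What to change.** In section 3.6.2:

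1. Name the confounder-adjusted model containing both exposures as the deciding model, with the unadjusted model as supportive.
2. State the unit of mechanical power. Make the primary estimate β_CP − β_MP per J/min (equivalently the ratio of odds ratios), with a 95% confidence interval from the joint covariance matrix. Report the contrast per SD as a prespecified sensitivity analysis.
3. Conclude 'less' only if the whole interval for the contrast lies below zero, and report both single odds ratios beside it.
4. State in advance how 'less' is read if mechanical power shows no harm, or if chemical power appears protective. Requiring the mechanical power odds ratio interval to lie above 1 is one option for the first case. It does not settle the second.

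The cost is SAP wording and a few lines of code. The price is precision: in every combination of the assumed inputs the contrast is less precise than at least one of the single odds ratios, so the conclusion may be less favourable. If the option in item 4 is adopted and the true log-odds are 0.05 (mechanical) and 0 (chemical), with N 4,000 and PPC 25%, the chance of concluding 'less' is 51 to 99.7% at a mechanical power SD of 4 J/min, but only 31 to 69% at an SD of 2. The contrast also assumes linear slopes, whereas section 2.2 hypothesises thresholds, so it should be read beside the planned splines.

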3. METHODS

3.1 Study Design and Population

We will perform a post hoc analysis of the previously combined dataset named 'Re-evaluation of the Effects of High PEEP with Recruitment Manoeuvres versus Low PEEP without Recruitment Manoeuvres During General Anaesthesia for Surgery' (REPEAT), registered at ClinicalTrials.gov: NCT03937375 on 3rd May 2019. This dataset merged the individual patient data from three RCTs, the 'High versus low positive end-expiratory pressure during general anesthesia for open abdominal surgery' (PROVHILO) study (registered with Controlled-Trials.com: ISRCTN70332574), the 'Individualized perioperative open-lung approach versus standard protective ventilation in abdominal surgery' (iPROVE) study (registered with ClinicalTrials.gov: NCT02158923) and the 'Effect of intraoperative high positive end-expiratory pressure with recruitment manoeuvres vs low PEEP on postoperative pulmonary complications in obese patients' (PROBESE) study (registered with ClinicalTrials.gov: NCT02148692).

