3.4.1 Primary Exposure

Chemical power calculated according to Lilien et al. [Lilien et al. 2023]:

Step 1: Estimation of local superoxide (O_2^-) production ($Pulm_{ROS}$) from lung oxygen consumption as a function of F_iO_2

$$Pulm_{ROS} = 1.7 * 10^{-5} + ((F_iO_2 - 0.21) * 1.63 * 10^{-4}) \text{ (mol/min)}$$

Step 2: Calculate chemical power (CP) from step 1 based on the first electron affinity of oxygen (141 kJ/mol).

$$CP = 141000 * Pulm_{ROS} \text{ (J/min)}$$

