3.6 Statistical Analysis

3.6.1 Descriptive statistics

The following variables will be descriptively presented, and additionally grouped by low, moderate, marked, and substantial chemical power (<25%, 25–50%, 50–75%, and 75–100% quantile of mechanical power), and considered as potential confounders (*) for the inferential statistics. Mean (standard deviation), median (interquartile range), frequency (percentage) will be reported based on variable type

and distribution.

Demographics

- Age *
- Sex *
- Height (cm)
- Weight (kg)
- BMI (kg/m^2) *
- ASA physical status *
- Trial *

Respiratory risk factors

- ARISCAT score *
- Preoperative SpO₂ *
- Respiratory infection within the past month *
- Anemia *

Coexisting conditions

- Heart failure *
- Chronic obstructive pulmonary disease *
- Cancer *

Surgery characteristics

- Preoperative hemoglobin (g/dL) *
- Type of surgery (abdominal versus non-abdominal) *
- Specific procedure
- Surgical approach (laparoscopic versus non-laparoscopic) *
- Year of surgery *
- Emergency or elective procedure *
- Duration of surgery *

Intraoperative mechanical ventilation parameters

- Tidal volume (V_t)
- Respiratory rate (RR)
- Peak pressure (P_{insp})
- Driving pressure (ΔP_{insp})
- Inspiratory oxygen fraction (FiO₂)
- Positive end-expiratory pressure (PEEP) *
- Exposures: chemical power and mechanical power
- Ventilation mode (VCV vs. PCV)

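### The 10% change-in-estimate rule has no reference model or joint check and no fit is named primary, so confounders that matter together can be dropped one by one

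*Combined protocol and SAP*

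**What the plan says.** Section 3.6.2 (Primary aim) states: "The regression model will be calculated with and without the above-mentioned confounders". It then contemplates, without committing to it, "exclusion of a potential confounder if its inclusion results in a change in the regression coefficients (beta) for both exposures of less than 10" per cent. It does not say which model the change is measured from, in what order covariates are examined, whether they are examined singly or together, whether any covariate is forced in, or whether the crude, full or reduced fit is the primary one.

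The candidates are the starred items in section 3.6.1. There are 19, among them Trial, BMI, anemia, "Preoperative hemoglobin (g/dL"), duration of surgery and "Positive end-expiratory pressure (PEEP").

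Secondary aim 2 adds its interaction term "in the multivariable regression model performed to evaluate the primary aim", so it inherits whichever model is chosen. The aim that this model serves is to "evaluate the relative contributions of intraoperative chemical and mechanical power on postoperative pulmonary complications" (section 2.1).

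**The concern.** The rule judges covariates by their separate effects on the coefficients, whereas confounding bias comes from what is left out together. Several weak confounders can each move the coefficients by less than 10% and yet matter jointly. Two overlapping covariates can each look dispensable because the other is still in the model. The documents show overlap of this kind. Anemia and preoperative hemoglobin are both starred. Trial overlaps with BMI, because the title of one of the three trials ends "vs low PEEP on postoperative pulmonary complications in obese patients" (section 3.1).

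The primary hypothesis compares two coefficients, so unequal confounding is what threatens it. Chemical power is computed "from lung oxygen consumption as a function of F_iO_2" (section 3.4.1), with no other patient-level input. Section 3.6.5 concedes that FiO2 use may be strongly confounded by pulmonary risk. If confounding of that kind is stronger for chemical than for mechanical power, dropping confounders distorts the comparison. The intervals from a selected model also take no account of the selection.

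PEEP raises a related question. It is a candidate covariate and also a component of mechanical power, so the rule would decide whether the mechanical-power odds ratio is estimated at fixed PEEP. The plan does not say which is meant.

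**Working it through.** **Inputs.** The 10% threshold, the requirement that both coefficients move by less than that, and the 19 candidates come from sections 3.6.1 and 3.6.2. The plan gives no sample size, event rate or correlations (section 3.6.4 has no power calculation), so there is no figure to reproduce and everything below is an illustration. Assumed: N 3,000; logistic model with intercept −0.8; 8 independent confounders, each with OR 1.15 per SD (log-OR 0.140); correlation of each with chemical/mechanical power 0.15/0.05; true coefficients 0.18 per SD for both exposures, so the true difference is 0.

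**Step 1: hand check of testing against the exposures-only model** (linear approximation on the log-odds scale).
- Correlation between exposures: 8 × 0.15 × 0.05 = 0.06.
- Covariance of the summed confounder effect with chemical power: 8 × 0.15 × 0.140 = 0.168. With mechanical power: 8 × 0.05 × 0.140 = 0.056.
- Bias if all 8 are omitted: chemical (0.168 − 0.06 × 0.056)/(1 − 0.06²) = 0.165; mechanical (0.056 − 0.06 × 0.168)/(1 − 0.06²) = 0.046. The spurious difference is 0.119.
- Exposures-only coefficients: 0.345 and 0.226. Adding any one confounder (same least-squares algebra, with the other seven omitted) gives 0.328 and 0.221, changes of −4.9% and −2.1%. Every confounder passes for exclusion.

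**Step 2: testing singly against the full model.** Dropping one confounder adds 0.140 × (0.15 × 0.9825 − 0.0075 × 0.05)/(0.8425 × 0.9825 − 0.0075²) = 0.025 to the chemical coefficient. Relative to the coefficient without the confounder this is 0.025/0.205 = 12%, just above the threshold. Most confounders are kept and sampling error drops some, so this reading is milder.

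**Step 3: simulation.** Repeated runs of a few hundred datasets per cell. A covariate is kept if either coefficient changes by 10% or more, and the interval for the difference uses the joint covariance of the two coefficients.

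| Reading of the rule | Difference (true 0) | 95% CI coverage |
|---|---|---|
| Singly, against exposures-only model | about 0.12 | 45–51% |
| Singly, against full model | about 0.03 | 81–82% |
| Stepwise, against previous model | 0.06–0.07 | 57–63% |
| Every reduced model against original full model | about 0.01 | 93–94% |
| Fixed full model, no selection | about 0 | 94–95% (93% in one run) |

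The first row agrees with the hand value of 0.119. With 300 datasets, the Monte Carlo standard error of a coverage near 50% is √(0.25/300) = 2.9 points, which accounts for the spread between runs.

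**Step 4: conditions under which the comparison is not harmed.** With equal confounding (0.15/0.15), each coefficient is biased by about 75% (against the exposures-only model) or 13% (singly against the full model), but the difference is unbiased with 94% coverage. With 4 of 8 confounders acting in the opposite direction, coefficient bias is at most 8% and coverage is 92–93%. When confounders are inter-correlated at 0.3, the order can switch: testing against the exposures-only model kept all 8 with no added bias, while testing singly against the full model did worse.

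**Step 5: an overlapping pair.** Assumed: correlation 0.9 between two confounders, log-OR 0.15 each, their combined score loading 0.3 on chemical and 0.1 on mechanical power, true coefficients 0.20. Dropping either one changes the coefficients by 0.6–2.4%. Dropping both changes them by +41% and +12%. This requires both to be tested against the full model at once; under stepwise removal the second would show the large change and stay.

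**Step 6: PEEP.** Section 3.4.2 defines driving pressure as Ppeak − PEEP. Hence Ppeak − 0.5 × (Ppeak − PEEP) = PEEP + 0.5 × driving pressure, and mechanical power = 0.098 × Vt × RR × (PEEP + 0.5 × driving pressure). In an assumed population with two PEEP levels, the mechanical-power OR per unit without versus with PEEP was 1.106 versus 1.105 if PEEP has no separate effect, 1.047 versus 1.105 if its log-OR is −0.05 per cmH2O, and 1.142 versus 1.106 if it is +0.03.

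**The case against.** The strongest reply is that the plan speaks of exclusion from a model that contains the confounders. This can be read as removing covariates while always comparing with the original full model. Under that reading the cumulative change is capped and the harm nearly vanishes (Step 3, fourth row). This stands: the damage depends on a choice the text leaves open, so it is not a demonstrated consequence of the rule.

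The rule is also softer than automatic deletion. Exclusion is only to be considered, and both coefficients must move by less than 10%. If the chemical coefficient is small, as the primary hypothesis expects, relative changes are large and covariates tend to be kept: with assumed true coefficients of 0.03 and 0.25, testing singly against the full model kept 7.9 of 8. That protection is real but partial. With the same coefficients, testing against the exposures-only model still gave 64% coverage. Discretion also adds an analyst's choice that the intervals do not reflect.

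The plan reports odds ratios per unit and no test of a difference, so the coverage figures describe a comparison implied by section 2.1 rather than a planned test. They are illustrations only.

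A reader might infer that the ranking of the two exposures will be wrong. The documents do not support that. Section 3.6.5 says FiO2 may be strongly confounded, but not that mechanical power is less so, and the 0.15/0.05 contrast is an assumption. A reader might also infer that PEEP is ignored or that selection on PEEP badly biases mechanical power. It is starred and therefore in the full fit. In simulations with assumed PEEP levels, the rule kept it in 87–97% of datasets where it mattered. The PEEP issue is an unstated estimand.

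**Conclusion.** The point holds as a defect of specification with a possible bias. The rule covers all 19 starred covariates, including Trial, without a reference model, order or joint check, and no fit is named primary for either the primary aim or secondary aim 2. Under single testing or stepwise removal against the previous model, joint omission can bias the exposure coefficients. The comparison between exposures is distorted only if confounding is unequal, which is plausible but not shown. The illustrated size runs from negligible to a spurious difference of about 0.12 per SD with roughly half the nominal coverage, and which end applies depends on the unstated reading and on assumed inputs. It should be changed because the fixed full model avoids the problem under every reading and is already planned. Confidence is medium, since no size can be derived from the documents themselves.

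**What to change.** - Delete the 10% exclusion rule.
- Name as primary the already planned model with all starred covariates, listed by name. Describe it as the full starred set rather than as baseline covariates, since it includes PEEP and duration of surgery.
- State that Trial is always included, because the complication definitions differ between trials (Table 1 in section 3.5.1; section 3.6.5).
- Use the same covariate set for the interaction model in secondary aim 2.
- Keep the model without confounders as a secondary display.
- Keep PEEP in the primary model as planned, state that the primary mechanical-power odds ratio is at fixed PEEP, and report the same model without PEEP as a sensitivity analysis.

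The cost is SAP wording, a few degrees of freedom and one extra model. Including PEEP also widens the interval for mechanical power; under assumed PEEP distributions its standard error rose 1.32- to 1.47-fold.

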We therefore aim to evaluate the effects of the chemical and mechanical power on postoperative pulmonary complications in combined data from three randomized trials that were designed to assess relationships between intraoperative ventilator settings, especially positive end-expiratory pressure (PEEP), and postoperative pulmonary complications. Additionally, we will test for harm thresholds and evaluate the interaction between chemical and mechanical power. Specifically, we seek to identify harm thresholds for chemical and mechanical power and will test the hypothesis that there is a synergistic interaction between chemical and mechanical power, such that lung injury is most apparent when the two are combined.

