2.2 Secondary Aims & Hypotheses

Secondary Aim 1: To identify the thresholds of harm for the associations of intraoperative chemical and mechanical power with postoperative pulmonary complications within seven days after surgery.

Secondary Hypothesis 1: The exposures to intraoperative chemical and mechanical power have thresholds of harm (inflection points) from which on the risk for postoperative pulmonary complications within seven days after surgery increases substantially.

Secondary Aim 2: To evaluate the interaction between the intraoperatively applied chemical and mechanical power on postoperative pulmonary complications within seven days after surgery.

Secondary Hypothesis 2: Chemical power-related harm largely depends on the concomitantly applied mechanical power, meaning that chemical power causes significantly more postoperative pulmonary complications within seven days after surgery when exposed to high intraoperative mechanical power.

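### Secondary Hypothesis 2 names no scale for synergy, and its only formal test, a logistic product term, does not estimate added complications

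*Combined protocol and SAP*

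**What the plan says.** The Background announces a test of the hypothesis that "there is a synergistic interaction between chemical and mechanical power, such that lung injury is most apparent when the two are combined". Section 2.2 puts it in terms of complications: "chemical power causes significantly more postoperative pulmonary complications within seven days after surgery when exposed to high intraoperative mechanical power". Neither place says whether the comparison is of odds, relative risks or absolute risks.

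Section 3.6.2 supplies the analysis for Secondary aim 2: "We will evaluate the interaction between chemical power and mechanical power by implementing an interaction term". The term goes into the primary-aim model, in which the two exposures' influence on PPCs "will be evaluated by multivariable logistic regression – estimating the odds ratios related to the effect of 1 unit increase in chemical or mechanical power". The product coefficient is therefore a ratio of odds ratios.

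Two further displays serve the same aim. The first is a stratified analysis: "we will analyse the effect of chemical and mechanical power on PPCs for 5 subsets of the study population stratified by chemical or mechanical power", repeated for each of four patterns. Section 3.6.3 reports it as "corresponding relative risks of PPC, calculated for each subsample", where "error bars represent the 95% confidence interval". The second is a "3D surface plot showing chemical and mechanical power on the x- and z-axes and the percentage of PPCs on the y-axis". Neither comes with an interaction contrast or test. No significance level or sidedness is given for the product term.

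**The concern.** The product term has as its null that the odds ratio for CP is the same at every level of MP. The section 2.2 wording most naturally asks something else: whether CP adds more complications among patients ventilated at high MP. Where CP already carries risk at low MP, these are different nulls. A product odds ratio of 1, or slightly below 1, can then sit alongside a larger number of added complications at high MP. At higher baseline risk the mismatch runs the other way.

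The other displays do not settle the matter. The stratified relative risks are on a ratio scale again, and none of the four patterns directly contrasts the CP effect at low MP with the CP effect at high MP. The percentage surface is on the absolute scale but has no estimate or interval.

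At stake is the reading of the result. A headline of no interaction, taken from the product term, could be understood by clinicians as meaning that CP adds no more complications at high MP, which the term does not estimate. With three scales on show and none designated, the scale could also be chosen after the results are seen.

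**Working it through.** **Inputs.** The documents give no patient number, event rate, effect size or power for this aim, so there is no figure of the plan's to reproduce. Everything below is assumed, in a simplified two-by-two layout (low or high CP, low or high MP): baseline risk p00 (both low) from 10% to 40%, odds ratio 1.5 for CP, 2 for MP, and product odds ratio 1 unless stated.

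**Formulas.** Odds = p/(1 − p) and p = odds/(1 + odds). With p10 = CP high only, p01 = MP high only and p11 = both high, CP adds p10 − p00 at low MP and p11 − p01 at high MP. The additive contrast is the second minus the first.

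**Step 1: one row in full.** At p00 = 10% the odds are 0.1111. CP alone: 0.1111 × 1.5 = 0.1667, so p10 = 14.3%. MP alone: 0.1111 × 2 = 0.2222, so p01 = 18.2%. Both: 0.1111 × 3 = 0.3333, so p11 = 25.0%. CP adds 4.3 points at low MP and 6.8 at high MP.

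**Step 2: across baseline risks, product odds ratio 1.**

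| Baseline | p10 | p01 | p11 | CP adds, low MP | CP adds, high MP | Product OR giving equal added points |
|---|---|---|---|---|---|---|
| 10% | 14.3% | 18.2% | 25.0% | 4.3 | 6.8 | 0.869 |
| 20% | 27.3% | 33.3% | 42.9% | 7.3 | 9.5 | 0.912 |
| 30% | 39.1% | 46.2% | 56.3% | 9.1 | 10.1 | 0.962 |
| 40% | 50.0% | 57.1% | 66.7% | 10.0 | 9.5 | 1.022 |

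The last column solves p11 = p01 + (p10 − p00). At 10%, p11 = 0.1818 + 0.0429 = 0.2247, with odds 0.2898, and 0.2898/0.3333 = 0.869. With product odds ratio 1 the contrast changes sign where the baseline odds equal 1/√(1.5 × 2) = 0.577, a risk of about 37%. With both odds ratios equal to 2, the odds are 1/2 and the risk is one third.

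**Step 3: opposite signs.** Take risks of 10%, 15% (CP only), 25% (MP only) and 33% (both). CP adds 5 points at low MP and 8 at high MP. The product odds ratio is [(0.33/0.67)/(0.25/0.75)] / [(0.15/0.85)/(0.10/0.90)] = 1.478/1.588 = 0.93. The relative risk for CP falls from 15/10 = 1.50 to 33/25 = 1.32, so the ratio measures both point down while the added complications go up.

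**Step 4: no CP effect at low MP.** If the CP odds ratio is 1 at low MP, CP adds 0 points there. Any CP odds ratio above 1 at high MP makes both the product odds ratio exceed 1 and the additive contrast positive, at every baseline risk.

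**Step 5: precision.** For the Step 3 risks with an assumed 3000 patients in four equal cells of 750, the standard error of the log product odds ratio is √[Σ 1/(750·p(1 − p))] = √0.0384 = 0.196, giving a 95% interval of about 0.63 to 1.37. The additive contrast of 3 points has standard error √(0.6261/750) = 2.9 points, hence about 18% power at an assumed two-sided 5% level. With both odds ratios 2, product odds ratio 1 and 10% baseline, the additive contrast has about 25%, 34% and 44% power at 2000, 3000 and 4000 patients.

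**The case against.** A reader might infer that the plan tests the wrong scale. The documents do not support that: section 2.2 speaks of more complications and the Background of synergy, and neither says absolute. Absolute risk is the natural reading, but it is a reading. What stands is that the scale is not stated.

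The plan's own rationale also narrows the problem. The Background suggests that the lung may tolerate oxygen when MP is low. If that were literally so, Step 4 applies and the scales cannot disagree in sign. However, section 2.2 says only that CP harm depends largely on MP, so a zero effect at low MP cannot be assumed.

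The percentage surface would let a reader see a larger absolute excess in the combined group. That is a fair partial answer, but a picture without an estimate or interval cannot carry the hypothesis.

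An additive measure has a weakness of its own. With two harmful exposures and low baseline risk, a logistic model gives a positive additive contrast even when the product coefficient is zero. Making it the sole test would tilt the analysis towards confirming the hypothesis. This objection stands, and it is why the product odds ratio should stay. It is also true that in the opposite-sign example neither estimate would be likely to reach significance, and that this is a secondary aim of a post hoc analysis which section 3.6.5 itself describes as associational.

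**Conclusion.** The point holds in a limited form. The hypothesis has no stated scale, the only formal test is on the odds-ratio scale, and no additive estimate with an interval is planned. Where CP already harms at low MP, a null or slightly negative product term can coexist with more added complications at high MP. On the assumed odds ratios of 1.5 and 2, the additive contrast is +2.5 points at 10% baseline risk, about +1 at 30% and −0.5 at 40%.

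Two stronger conclusions might be inferred and are not supported. One is that a null product term would reject synergy: it would only fail to show interaction in odds, and the plan has no rule for declaring the hypothesis refuted. The other is that the planned test is bound to understate synergy: the direction depends on baseline risk and on the CP effect at low MP, and the documents give neither. The algebra is certain; its consequence for this dataset is not. This is a cheap improvement worth making before analysis, not a flaw that invalidates the aim.

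**What to change.** In section 3.6.2, Secondary aim 2:

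- Keep the product odds ratio as the multiplicative-scale result.
- Prespecify beside it an additive estimate from the same adjusted model with the product term. Compute the standardised PPC risk difference for a fixed CP contrast (25th to 75th percentile), once with MP at its 25th and once at its 75th percentile. Report the difference between the two with a bootstrap 95% confidence interval.
- State in advance that a conclusion about more complications is read from the additive estimate and a conclusion about odds from the product odds ratio, and that a non-significant product term is not evidence against synergy in risk.

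The cost is a short change of wording and a few lines of post-estimation code; no new data or different model is needed. The downside is one more interaction estimate, probably imprecise, whose sign partly reflects the logistic link and the baseline risk. Both scales must therefore be shown together. The percentiles are a convention and could be replaced by other values, provided they are fixed beforehand.
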